There are twelve DMTs currently approved by the Food and Drug Administration (FDA) to treat patients with MS. All of these therapies impact the immune system and, in the aggregate, have been shown to decrease new inflammatory lesions (T2 hyperintense lesions) [see review by Tullman; (Tullman, 2013)]. Though we are able to decrease the potential for new injury, there are no medications that are shown to decrease the likelihood of black hole formation (lesion evolution) once the T2 lesion forms. If cerebral perfusion is an important contributor to tissue repair then MS lesions within hypoperfused areas might be more likely to develop permanent tissue loss. In this scenario, medications that encourage cerebral perfusion might alter the evolution of new MS plaques and diminish clinical disability progression.

To test this hypothesis, we propose to utilize ACZ, an existing medication with a well-established safety and tolerability profile that has been shown to enhance cerebral perfusion ("Acetazolamide Tablets | Drug Summary | PDR.net," n.d.; Lim et al., 2001; Stewart et al., 2002). To the best of our knowledge, ACZ has not been previously evaluated as a potential therapy in patients with MS. This study will determine if the novel application of long-term ACZ therapy in subjects with MS improves cerebral perfusion resulting in a smaller proportion of MS lesions that evolve to form the persistent black holes that reflect permanent tissue damage. Stage 1a of the study will define the magnitude of change in regional cerebral perfusion following acute IV ACZ therapy. Stage 1b will determine the degree to which short-term use of divided daily oral doses of ACZ improves global and regional

cerebral perfusion in subjects with MS. Finally, Stage 2 of the study will determine the effect of long-term oral ACZ on lesion evolution.

Rationale for Doses Selected

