At the end of week 24, patients initially randomized to Treatment B will take 1000 mg extendedrelease ACZ capsules. Similar imaging and clinical evaluations will be performed for the second 24week period. All subjects will discontinue drug at week 48 and obtain a follow-up clinical visit two weeks later. Based upon established pharmacokinetics, the half-life of drug is between 60-75 hours and one would expect insignificant levels within two weeks of discontinuation.

To maintain blinding, patients, evaluating clinicians and MRI analysts will not be informed of treatment assignment or sequence of scans.

We anticipate that sustained increases in regional cerebral perfusion over 6 months will result in improved tissue integrity as measured using diffusion tensor metrics and fewer MS lesions that evolve to persistent black holes.

HYPOTHESIS AND OBJECTIVES

Hypothesis

The underlying hypothesis of this proposal is that long-term therapy with ACZ will improve cerebral perfusion in subjects with MS and this improved perfusion will result in improved tissue integrity in a proportion of MS lesions. To test this hypothesis, subjects will be treated with ACZ, a currently FDA approved agent previously shown in healthy controls to increase cerebral perfusion (Sullivan et al., 1987; Vagal et al., 2009). Subjects will be scanned at various time points (see sections 4 and 6.3) and quantitative MRI metrics will be used to evaluate lesion evolution during and after discontinuation

of treatment.

Primary & Key Secondary Objective

Determine the degree to which divided daily doses of ACZ improves global and regional cerebral perfusion in subjects with MS.

Study subjects will obtain serial MRI scans prior to, during and after therapy (see sections 4 and 6.3). Cerebral blood flow will be measured using an optimized pCASL technique as described by Aslan (Aslan et al., 2010). This will allow us to test the first component of our hypothesis that treatment with ACZ will result in increased regional and/or global perfusion.

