The primary endpoint of this study will be to determine if therapy with oral divided-dose ACZ administered each day for week-long period results in at least 15% increase in CBF. Studies have shown between 10% - 15% decrease in cerebral perfusion in patients with relapsing MS (Adhya et al., 2006). Therefore, increases in CBF of at least 15% might result in change to lesion evolution. Baseline CBF measures will be compared to measures obtained at each dose escalation step using paired *t* test and Mann-Whitney test.

Determine the effect of long-term oral ACZ on lesion evolution. The key secondary endpoint of this study is to determine if long-term use of oral daily divided-dose with ACZ improves tissue integrity in a proportion of MS lesions.

MRI scans will be segmented using into white and gray matter, T2 and T1 lesion components and contrast-enhancing lesion component. Expert raters (I.V., S.D., L.F.), who are blinded to treatment arm (see section 6.1) will perform quality control of the automated segmentation and obtain quantitative measures of cerebral perfusion. The number and volume of T2 hyperintense and T1 hypointense lesion will be determined using MRIAP. The ratio of T1 hypointense/T2 hyperintense lesion will be determined for baseline and each crossover period and correlated with CBF, CBV and MTT measures obtained at similar times using the Spearman rank correlation.

Diffusion tensor imaging (DTI) is a reliable, validated technique that quantitatively measures molecular diffusivity within tissue and provides information about its microstructural integrity. DTI will be used to monitor tissue integrity and correlate change with increases in CBF following ACZ.

Tertiary Objectives

Several studies have quantitated transverse and longitudinal relaxation times within lesions and normal-appearing white matter and gray matter. These studies have shown that changes in both transverse and longitudinal relaxation can precede lesion formation and possibly better evaluate lesion evolution as compared to black hole volumes (Papadopoulos et al., 2010; van Walderveen et al., 1999a; Walsh et al., 2014; Warntjes et al., 2013). We will manually delineate regions of interest within lesions to obtain T2 and T1 relaxometry metrics. Lesions within areas with greatest change in CBF will be compared with those with least change. We anticipate a correlation between relaxometry measures and areas with varying CBF.

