MRI scans for each subject will be assigned a unique non-contiguous random ID using a 5-digit random number generator and all imaging raters (I.V., S.D., L.F.) will be blinded to treatment arm. A semi-automated, previously validated tissue segmentation software (FreeSurfer v5.3, https://surfer.nmr.mgh.harvard.edu/) will be used to determine T2 hyperintense (lesion) and T1 hypointense (black hole) volumes. A separate expert rater (K.H.) will review and analyse DTI images. An expert rater (I.V), blinded both to treatment arm and sequence of scan acquisition, will perform quality control checks of software segmentation.

Image analysis to determine regional and global CBF as well as atrophy will be performed by additional qualified expert raters (S.D., L.F., K.H.) who are blinded to the treatment arm.

Contraception and Pregnancy Testing

Female participants must use effective means of birth control for the duration of the study. Effective birth control is defined as refraining from all acts of vaginal intercourse (abstinence), consistent use of birth control pills, tubal sterilization or male partner who has undergone vasectomy, placement of an IUD (intrauterine device), or use of a diaphragm with contraceptive jelly and/or condoms with contraceptive foam with every act of intercourse. Study participants will receive urine pregnancy tests prior to ACZ and as scheduled in the trial schedule (see section 4).

Study Visits and Procedures

Stage 1a:

Screening Visit – Subjects will receive a complete medical and neurological examination. In addition, all subjects will obtain CBC, CMP and, if female, urine pregnancy test.

Subjects will receive non-contrast MRI brain with scout, 3DT1 and pCASL sequences immediately prior to infusion of IV ACZ. The scout sequence is used to establish proper subject orientation and slice prescription and requires less than 5 minutes. The 3DT1 is a rapid sequence that allows for proper registration between scans and will be obtained after the scout images and again if the patient is removed from the MRI gantry. Finally, pCASL sequences will be performed to determine CBF. The group of sequences including pCASL will collectively require about 12 minutes.

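### The stated T1/T2 lesion outcomes are per-scan number, volume and ratio, which do not identify the proportion of lesions that become persistent black holes, and no lesion-fate analysis is given

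*Combined protocol and SAP*

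**What the plan says.** **The question.** Rationale for the Study Purpose says the study will determine whether long-term ACZ improves perfusion, "resulting in a smaller proportion of MS lesions that evolve to form the persistent black holes that reflect permanent tissue damage". The Stage 3 text under Rationale for Study Design anticipates "fewer MS lesions that evolve to persistent black holes". Summary of Study Design and Safety Monitoring Plan repeat the aim as lesions turning into permanent black holes. The key secondary endpoint is whether ACZ "improves tissue integrity in a proportion of MS lesions".

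**The measurement.** Under Primary & Key Secondary Objective, "The number and volume of T2 hyperintense and T1 hypointense lesion will be determined using MRIAP" and "The ratio of T1 hypointense/T2 hyperintense lesion will be determined for baseline and each crossover period". Summary of Study Design and Randomization and Blinding list segmented T1 and T2 lesion volumes.

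**The blinding.** Randomization and Blinding states that "MRI scans for each subject will be assigned a unique non-contiguous random ID using a 5-digit random number generator". For Stage 3, "MRI analysts will not be informed of treatment assignment or sequence of scans".

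**The analysis.** Sample Size and Statistical Methods applies mixed models to all outcomes and describes them for CBF, for MD and FA by region and by white matter with and without lesions, and for a tertiary composite that it does not define. It contains no analysis of what becomes of a lesion.

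**The concern.** Whether a lesion evolved can be known only by comparing the same lesion on an earlier and a later scan. Per-scan number, volume and ratio describe net lesion load. Resolution of some holes and formation of others can cancel, leaving the totals unchanged. The protocol also does not say when a hole counts as persistent or which lesions are at risk.

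Two things are at stake. First, a null result on net load could be reported as no effect on evolution. The pilot is meant to identify the best outcome measures for a phase 3 trial, so that misreading would carry forward. Second, if lesion fate is worked out later, the at-risk set and the persistence rule would be chosen after the data are in. Timing makes this choice matter, because placebo patients start ACZ after the week-24 scan.

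**Working it through.** The documents state no figure for lesion evolution, so there is none to reproduce.

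**1. What two sets of per-scan totals identify.** Take N T2 lesions, the same ones on both scans, with a black holes on the first scan and b on the second. Without a link between lesions, the number of original holes that persist can be anything from max(0, a + b − N) to min(a, b). Newly converted lesions are b minus that number, out of N − a. The counts below are assumed.

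| N | a | b | T1/T2 ratio | Original holes persisting | Other T2 lesions converted |
|---|---|---|---|---|---|
| 20 | 8 | 8 | 0.40, 0.40 | 0 to 8 of 8 (0% to 100%) | 0 to 8 of 12 (0% to 67%) |
| 20 | 8 | 4 | 0.40, 0.20 | 0 to 4 of 8 (0% to 50%) | 0 to 4 of 12 (0% to 33%) |
| 20 | 12 | 12 | 0.60, 0.60 | 4 to 12 of 12 (33% to 100%) | 0 to 8 of 8 (0% to 100%) |

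The ratio uses the same totals and adds nothing. Volumes carry no lesion link.

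**2. Placebo-controlled follow-up.** The controlled period ends at week 24. A lesion present at week 0 has 24 weeks. One first seen on the week-12 contrast scan has 24 − 12 = 12 weeks, and one first seen at week 24 has none. A new T2 lesion visible on the non-contrast week-6 scan would have 18.

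**3. Illustration of the information lost.** The only input from the protocol is a persistence of up to 40% (General Introduction) and 25 per arm (half of the 50 analysed). Assumed: ACZ halves persistence to 20%; k = 1 or 2 evolving lesions per patient (Poisson); 0.5 new lesions per patient in each arm (Poisson); lesions independent; two-sided 5% test.

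- *Change from baseline in the total count.* Stable old holes cancel. Change = new lesions − resolved lesions. The arms differ by 0.2k. The variance is 0.6k + 0.5 on placebo and 0.8k + 0.5 on ACZ.
  - k = 1: z = 0.2 / √(2.4/25) = 0.2/0.310 = 0.65, power about 9%.
  - k = 2: z = 0.4 / √(3.8/25) = 0.4/0.390 = 1.03, power about 18%.
- *Lesion fates, 40% versus 20%.* With 25k lesions per arm, z = 0.2 / √(2 × 0.3 × 0.7 / 25k).
  - k = 1: z = 1.54, power about 34%.
  - k = 2: z = 2.18, power about 59%.

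**4. The at-risk set matters.** If every lesion that is T1-hypointense at week 0 is counted, with an assumed 10 old holes and 1 evolving lesion per patient, persistence is 10.4/11 = 94.5% versus 10.2/11 = 92.7%. By simulation (old holes negative binomial, mean 10, dispersion 2), lesion-level power then falls to about 17% for k = 1 and 30% for k = 2.

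**The case against.** **The plan has other lesion and tissue measures.** This stands. Tertiary Objectives places manual regions of interest inside lesions for relaxometry and compares lesions by CBF change. The Stage 3 rationale measures tissue integrity by diffusion tensor imaging, and the statistical section models MD and FA over time. A reader might infer that lesions are measured only as totals, and that is not so. None of these measures, however, says whether a lesion became a black hole.

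**The coding and order masking might be blamed.** A reader might infer that separately coded, order-masked scans make lesion tracking impossible. The documents do not support that. The planned models use time, group-by-time and a patient random intercept, so the codes must be undone after reading anyway, and images for registration are acquired at each visit. What is missing is a written matching step.

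**Totals might be thought no better than chance.** A test of raw week-24 totals has about 5% power in the illustration. The plan, however, models change over time, and change from baseline is the fair comparator. Its power is low, at about 9% to 18%, but above 5%.

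**Black-hole fate is not the powered outcome.** This is true: the sample size concerns global CBF, and much of the rest is exploratory. It limits the weight of the point but does not remove it, since lesion evolution is the stated purpose and has no defined variable.

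**Conclusion.** The point holds. The proportion of lesions evolving to persistent black holes is asked about in several sections, but it is not identified by the stated T1/T2 outcomes and has no analysis. The non-identification follows from the bounds alone and needs no power assumption; the assumed counts only show how wide the range can be, up to 0% to 100%.

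The power figures are illustrations. They rest on lesion counts and an effect that the documents do not give, and clustering of lesions within patients would lower the lesion-level values. They suggest a substantial loss of information when change in totals stands in for lesion fate. They do not show that the trial would detect a real effect on fate with 25 per arm.

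The primary CBF analysis is unaffected. This is a change the sponsor should make before unblinding.

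**What to change.** - Keep per-scan segmentation and quality control blind as written, and lock the masks.
- Then relink each patient's masks in time order by program, using the registration images already acquired, with treatment arm still masked.
- Define two at-risk sets at week 0 and report them separately: (a) gadolinium-enhancing lesions, classed at week 24 as T1-hypointense or not; (b) T2 lesions not T1-hypointense at week 0, classed at week 24 as converted or not. State that (b) shows conversion at one scan, not proven persistence.
- Report chronic non-enhancing black holes present at week 0 apart from both sets, so that they do not dilute the comparison.
- Compare arms at week 24, before placebo patients start ACZ, with a logistic mixed model with a patient random intercept.
- Report lesions first seen after week 0 descriptively.
- Keep number, volume and ratio as supportive measures, analysed as change from baseline.
- Reconcile the segmentation software, which is MRIAP under the objectives and FreeSurfer under blinding.

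**Cost.** Protocol and SAP wording and a small matching step on existing scans, with no new scan or patient. Patients with no at-risk lesion do not contribute, so precision may be low and the result should be labelled exploratory.

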CBC, CMP		Х	Х	Х	Х	Х	Х	Х	Х	X	
Urine pregnancy*		Х									
DSC MRI		Х		Х		Х		Х		Х	
pCASL MRI		Х	х	Х	Х	Х	X	Х	Х	X	Х
MSFC		Х	Х	Х	Х	Х	Х	Х	Х	Х	Х
EDSS		Х	Х	Х	Х	Х	Х	Х	Х	Х	Х
MFIS, MSWS-12		Х	х	Х	Х	Х	Х	Х	Х	X	Х
Blood Sample		X	х	Х	Х	X	Х	X	Х	X	Х
* Female par	rticipants v	who have alrea	ady beer	n evalua	ted for pi	regnancy	y will not	be retes	ted unle	ss otherwise	

* Female participants who have already been evaluated for pregnancy will not be retested unless otherwise indicated

- Additional CBC,CMP will be performed if measured ALT/AST > 1X ULN or if other alterations above baseline
- EDSS Expanded disability status scale
- MSFC Multiple Sclerosis Functional Composite Scale

STUDY DESIGN

Summary of Study Design

The initial stages of this study are designed as a proof of principle to show that ACZ therapy improves cerebral perfusion in MS subjects. The final stage of this study is a prospective crossover design to evaluate the potential for ACZ to persistently enhance cerebral perfusion and impact the evolution of T2 hyperintense MS lesions into permanent black holes. This pilot study is anticipated to lead to a larger randomized phase 3 clinical trial.

Participants will be recruited from the MS patient population seen at the UTP practice. The MS Clinic is a National MS Society affiliated comprehensive and coordinated center for MS care and a member of the Consortium of MS Centers. This clinic evaluates approximately 2700 MS patients per year. Given the safety and tolerability of study drug, we anticipate recruitment of two MS subjects each month for all stages of this study.

Stage 1a - This stage will determine the degree of change, temporal kinetics and difference between various regions in cerebral perfusion after IV ACZ in subjects with MS.

In total, this portion of the study is anticipated to be complete within 2.5 months. ACZ therapy and all image acquisition will be completed on the same day for subjects enrolled in stage 1a.

As all subjects will be treated with IV ACZ, the image analyst will be unblinded during this stage. Cerebral perfusion measures will be determined by S.D.

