Visit 3 – Subjects will receive a complete medical and neurological examination, MSFC & EDSS evaluation as well as patient-reported clinical disability measures (MFIS & MSWS-12) and will be asked questions to ascertain tolerability to daily therapy. All subjects will obtain MRI brain with and without gadolinium contrast utilizing the sequences described above.

Visit 4 – Subjects will receive a complete medical and neurological examination, MSFC & EDSS evaluation as well as patient-reported clinical disability measures (MFIS & MSWS-12) and will be asked questions to ascertain tolerability to daily therapy. All subjects will obtain MRI brain without gadolinium contrast utilizing the sequences described above except for DSC sequence.

Visit 5 – Subjects will receive a complete medical and neurological examination, MSFC & EDSS evaluation as well as patient-reported clinical disability measures (MFIS & MSWS-12) and will be asked questions to ascertain tolerability to daily therapy. All subjects will obtain MRI brain with and without gadolinium contrast utilizing the sequences described above.

Upon completion of the MRI scan, all subjects will be instructed to discontinue treatment.

Stage 3: Screening Visits and Procedures

The screening visit will occur within one week of study entry. Subjects with relapsing forms of multiple sclerosis without evidence of other neurologic or cardiovascular disease will be recruited for this study.

Subjects will provide a complete medical history and undergo a complete medical and neurological exam. Blood tests (complete blood counts [CBC] and complete metabolic panel [CMP]) will be obtained from every study subject. Female subjects will also be given a urine pregnancy test during the screening visit. In addition, all subjects will undergo a screening MSFC and EDSS (Kurtzke, 1983).

All subjects will be required to discontinue use of herbal supplements for the duration of the study. Finally, both male and female subjects will be counselled on the use of contraceptive methods (see section 6.2) during the study.

Screening Visit – Subjects will receive a complete medical and neurological examination and obtain screening EDSS evaluation. In addition, all subjects will obtain CBC, CMP and, if female, urine pregnancy test.

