Visit 1 – Subjects will be randomized to receive Treatment A or Treatment B first for the initial 24 weeks. Subjects will receive MRI brain with and without gadolinium contrast utilizing MRI sequences as detailed in Stage 2a.

Subjects will be contacted by telephone or email monthly to document tolerability and encouraged to report any AE occurring with drug at any point during the study.

Visit 2 – Subjects will receive a complete medical and neurological examination, MSFC & EDSS evaluation as well as patient-reported clinical disability measures (MFIS & MSWS-12) and will be asked questions to ascertain tolerability to daily therapy. All subjects will obtain MRI brain without gadolinium contrast utilizing the sequences described above except for DSC sequence.

Visit 3 – Subjects will receive a complete medical and neurological examination, MSFC & EDSS evaluation as well as patient-reported clinical disability measures (MFIS & MSWS-12) and will be asked questions to ascertain tolerability to daily therapy. All subjects will obtain MRI brain with and without gadolinium contrast utilizing the sequences described above.

Visit 4 – Subjects will receive a complete medical and neurological examination, MSFC & EDSS evaluation as well as patient-reported clinical disability measures (MFIS & MSWS-12) and will be asked questions to ascertain tolerability to daily therapy. All subjects will obtain MRI brain

without gadolinium contrast utilizing the sequences described above except for DSC sequence.

Visit 5 – Subjects will receive a complete medical and neurological examination, MSFC & EDSS evaluation as well as patient-reported clinical disability measures (MFIS & MSWS-12) and will be asked questions to ascertain tolerability to daily therapy. All subjects will obtain MRI brain with and without gadolinium contrast utilizing the sequences described above.

Upon completion of the MRI scan, subjects previously treated with Treatment B will start Treatment A and all subjects will continue on Treatment A for the remaining 24 weeks of the study.

Visit 6 – Subjects will receive a complete medical and neurological examination, MSFC & EDSS evaluation as well as patient-reported clinical disability measures (MFIS & MSWS-12) and will be asked questions to ascertain tolerability to daily therapy. All subjects will obtain MRI brain with and without gadolinium contrast utilizing the sequences described above.

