A comprehensive list of AEs provides previously reported and/or potential AEs associated with ACZ. Common AEs are in **bold**. They include **paresthesias**, particularly a "tingling" feeling in the extremities, hearing dysfunction or tinnitus, loss of appetite, **taste alteration** and gastrointestinal disturbances such as **nausea**, **vomiting**, **dyspepsia and diarrhea**, polyuria, and occasional instances of **drowsiness/fatigue** and confusion. Metabolic acidosis and electrolyte imbalance may occur. Transient myopia has been reported though this condition invariably subsides upon diminution or discontinuance of the medication.

Other occasional adverse reactions include urticaria, melena, hematuria, glycosuria, hepatic insufficiency, flaccid paralysis, photosensitivity and convulsions.

Collecting, Recording and Reporting of Adverse Events

Recording AEs – The treating physician will be the principal investigator ([name]). The treating physician will oversee subject management including all assessments and treatment of adverse events and disease relapses should they occur. The treating physician will make decisions regarding determining relatedness and grading severity of all AEs. The treating physician will be blinded to treatment arm unless necessary to assess safety concern.

Maintaining documentation and reporting AEs – The clinical coordinator ([name]) will assist in subject management, maintain documentation including all subject case report forms (unanticipated problems tracking log) and will submit all reports to the IRB per UTSHC-Houston policy

Safety Monitoring Plan

This pilot study will determine the extent to which improved cerebral perfusion from oral ACZ therapy reduces the evolution of MS lesion into permanent black hole. Subjects will be monitored, as per protocol, by the treating physician for clinical MS activity. However, to our knowledge there are no case reports or other studies to suggest that therapy with ACZ will contribute to new lesion formation or clinical relapse. As such, we do not anticipate an increase in relapse frequency secondary to ACZ.

Subjects will be monitored by the treating physician for AEs and serious AEs (see section 9.1). The frequency and grade of AEs will be documented and treatment arm(s) adjusted or discontinued as needed. Subjects can withdraw consent for study at any point and for any reason during the trial.

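### Stage 3 women randomised to placebo first start acetazolamide at week 24 on a pregnancy test that is 24 to 25 weeks old

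*Combined protocol and SAP*

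**What the plan says.** Section 6.2 (Contraception and Pregnancy Testing) gives the general rule: "Study participants will receive urine pregnancy tests prior to ACZ and as scheduled in the trial schedule". It names no visit and refers to the schedule in section 4. The same section requires contraception throughout: "Female participants must use effective means of birth control for the duration of the study". Exclusion criterion 16 bars a woman with a positive test at screening.

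The Stage 3 table in section 4 marks a urine pregnancy test once, at week 0 (Visit 1). Its footnote reads: "Female participants who have already been evaluated for pregnancy will not be retested unless otherwise indicated".

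The Stage 3 visit text places the baseline test slightly earlier: "Female subjects will also be given a urine pregnancy test during the screening visit". On the timing of that visit: "The screening visit will occur within one week of study entry". The descriptions of Visits 2 to 11 mention no pregnancy test.

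The Visit 5 (week 24) description sets out the treatment change: "Upon completion of the MRI scan, subjects previously treated with Treatment B will start Treatment A and all subjects will continue on Treatment A". Completing the scan is the only step named before the change.

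**The concern.** Testing at baseline only suits a design in which every subject starts drug at baseline. Stage 3 has a delayed start, so half of its design involves a first exposure 24 weeks later. A positive test keeps a woman out at screening, but no equivalent check guards the first dose in the placebo-first arm.

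The stake is fetal exposure. The label for the extended-release capsules, reproduced in the protocol, places the drug in Pregnancy Category C, reports limb defects in mice, rats, hamsters and rabbits, and confines use in pregnancy to cases where benefit outweighs the risk to the fetus. In MS no benefit has been established: the protocol says it knows of no earlier evaluation of ACZ as an MS therapy. A pregnancy that began in the placebo period and went unnoticed could be exposed from week 24 onward.

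**Working it through.** **Age of the last scheduled test at first ACZ dose**

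Inputs: the test is at week 0 (section 4 table) or week -1 (Stage 3 screening text). The first dose is at week 0 for early-start women and week 24 for placebo-first women (Visit 5 text).

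Age of test = week of first dose minus week of last scheduled test.

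| Stage 3 arm | Test date from table | Test date from visit text |
|---|---|---|
| Early start | 0 - 0 = 0 weeks | 0 - (-1) = 1 week |
| Placebo first | 24 - 0 = 24 weeks | 24 - (-1) = 25 weeks |

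In the other stages, first exposure follows the stage's own scheduled test closely: about one week in Stages 1a and 1b (screening at day -7), 0 to 4 weeks in Stage 2a, and 0 to 1 week in Stage 2b. Only the placebo-first arm departs from this.

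**Tests after baseline.** The Stage 3 table has nine time points after week 0 (weeks 6, 12, 18, 24, 30, 36, 42, 48 and 50). None of the nine has a pregnancy test.

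**How the footnote can be read.** The natural reading is that a woman tested at this stage's screening visit need not be tested again at week 0. A broader reading would accept a test from an earlier stage, since the protocol lets a subject join several stages. It is not far-fetched: the Stage 1b table attaches the same footnote to a row whose only test is at screening, where it can only refer to a test done before that visit. For a woman moving straight from the 24-week Stage 2b (test at its week 0 or -1), the broader reading gives:

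- at Stage 3 week 0: at least 24 weeks;
- at Stage 3 week 24: at least 24 + 24 = 48 weeks.

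This is secondary. The Stage 3 text asks for a test at that stage's screening visit, and the 24-to-25-week result does not depend on the broader reading.

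**Women concerned.** Inputs: 60 subjects and 18% dropout (section 11); a female-to-male ratio of nearly 4:1 (Rationale for Study Population), taken as 4/5 = 80% women. Equal allocation is assumed because the plan does not state a ratio.

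- Placebo-first subjects: 60 / 2 = 30.
- Women among them: 30 x 0.80 = 24.
- If all dropout falls before week 24: 24 x 0.82 = 19.7, about 20.
- Placebo time: 24 x 24/52 = 11.1 woman-years, or 19.7 x 24/52 = 9.1.

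These are upper head-counts. Women not of childbearing potential, or protected by sterilisation, should be subtracted. The documents give no pregnancy rate, so no number of pregnancies is estimated.

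**The case against.** The strongest reply is that section 6.2 already covers the case. It asks for a test before ACZ as well as tests per schedule. If the baseline test met both parts, the first would add little, so it could mean a test before each woman's own first dose. That reading is possible. But the baseline test also satisfies the words, neither the table nor the Visit 5 text provides another, and the footnote points the other way. Site staff working from the schedule would not do the test. If it is intended, it needs to be written down.

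The second reply is mitigation, and much of it stands. Contraception is mandatory, and each visit at weeks 6, 12, 18 and 24 includes a history and physical: "Subjects will receive a complete medical and neurological examination". There are monthly contacts, and the footnote's exception permits testing on suspicion. Still, the visit and contact descriptions speak of tolerability and adverse events, not pregnancy, and an examination can miss an early pregnancy. The protocol also requires a baseline test on top of contraception, so it does not itself treat contraception as enough for starting the drug.

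Blinding ("The treating physician will be blinded to treatment arm unless necessary to assess safety concern") is no obstacle to testing on suspicion, since a physician can test any woman without knowing her arm. It does mean that a test aimed only at women about to start ACZ would reveal assignment, so both arms should be tested.

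Three further points are fair. The label does not ask for repeat pregnancy tests. Early-start women also have no scheduled test while on drug. How often to retest during treatment is largely a design choice. A test before first exposure is a narrower matter, and there the plan departs from its own practice.

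**Conclusion.** The concern holds. Followed as written, Stage 3 gives placebo-first women their first ACZ dose with a last scheduled pregnancy test 24 to 25 weeks old, against 0 to 1 week in the early-start arm. The interval rests only on the schedule and the visit text. The count of at most about 24 women (about 20 after full early dropout) rests on 1:1 allocation and 80% women, neither of which the plan states for this trial. It is a count of women concerned, not a risk.

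This is a safety gap in the schedule rather than a contradiction in the rules. It has no bearing on sample size, power or the primary analysis. It should be corrected because the possible harm is preventable and the remedy is cheap.

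**What to change.** 1. Add a urine pregnancy test at Visit 5 (week 24) to the Stage 3 table and visit text, for all women of childbearing potential in both arms. Require a negative result before Treatment A is dispensed. Testing both arms protects the blind and gives early-start women their only scheduled test during 48 weeks on ACZ.
2. Limit the Stage 3 footnote so that only a test from that stage's own screening visit can stand in for the week-0 test, and exempt the week-24 test from it.
3. Make the table and the visit text agree on whether the baseline test is at screening or week 0.

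The cost is at most about 60 x 0.80 = 48 urine tests, at a visit that already includes an examination, CBC/CMP and MRI, plus edits to the table, footnote and visit text.
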